#### 2.7. DURATION OF THE STUDY

All cases will be followed up to 10 years. It is expected that the enrollment will be completed in 1 year, the total duration of the study is 11 years.

## 3. SELECTION AND WITHDRAWAL OF SUBJECTS

#### 3.1 INCLUSION CRITERIA

Patients will be included in this study if they received Vanguard knee with E1 Bearing per the approved indications for use for Vanguard Knee. Specifically

- Painful and disabled knee joint resulting from osteoarthritis or traumatic arthritis where one
  or more compartments are involved.
- Correction of varus, valgus, or posttraumatic deformity.
- Correction or revision of unsuccessful osteotomy

#### 3.2 EXCLUSION CRITERIA

Exclusion Criteria for this study should comply with the stated contraindications on package inserts of Vanguard™ Knee and the E1™ Tibial Bearing. These indications are stated below:

Absolute contraindications include: infection, sepsis, osteomyelitis, and failure of a previous joint replacement.

#### Relative contraindications include:

- Uncooperative patient or patient with neurologic disorders who are incapable of following directions,
- Osteoporosis
- Metabolic disorders which may impair bone formation,
- Osteomalacia
- Distant foci of infections which may spread to the implant site,
- Rapid joint destruction, marked bone loss or bone resorption apparent on roentgenogram,
- Vascular insufficiency, muscular atrophy, neuromuscular disease,
- Incomplete or deficient soft tissue surrounding the knee.

## 3.3. SUBJECT WITHDRAWAL where appropriate

It is recognized that the subject's participation in this trial is entirely voluntary, and that she/he may refuse to participate and may withdraw from participation at any time without jeopardy to any future medical care. It is also recognized that the investigator, at his/her discretion, may withdraw a subject from this study based upon his/her professional judgment. In event of subject withdrawal, applicable local procedures should be followed

## 4. PROTOCOL DEVIATION MANAGEMENT AND REPORTING

Protocol deviations are unplanned and unintentional events. However, if data is collected and represents a protocol deviation, this should be documented on the protocol deviation form.

Protocol deviations must be reported to the Sponsor and the Ethical Committee as locally required. Any further reporting required of the Ethical Committee should be completed.

#### 5. ADVERSE EVENT MANAGEMENT AND REPORTING

A record of all adverse events, including details of the nature, onset, duration, severity, relationship to the device, relationship to the operative procedure and outcome, will be made and provide to the study sponsor.

The subject will be questioned about any adverse event(s) at each subsequent follow-up assessment visit.

Serious Adverse Events that are related to the device should be reported to the Ethical Committee and

Sponsor as soon as possible. These include any untoward medical occurrences that result in death, are life threatening, require in patient hospitalization, or prolongation of existing hospitalization, result in persistent or significant disability/incapacity, or resulted in a congenital anomaly/birth defect.

#### 6. STATISTICAL ANALYSIS PLAN

#### 6.1. SAMPLE SIZE CALCULATION

200 Cases is determined based on a confidence interval around the mean KSS objective score at 1 year.

The width of confidence interval is 5 points. The standard deviation is 18 points.

Total number of cases = 199 cases which is rounded to 200 cases.

#### 6.2. DETAILED DESCRIPTION OF RANDOMIZATION where appropriate

NA

#### 6.3. DETAILED DESCRIPTION OF BLINDING where appropriate

NA

#### 6.4. HANDLING OF MISSING AND INCOMPLETE DATA

Attempt will be made to ensure that patients come back for scheduled follow-up evaluations. In case of missing data, for clinical outcome scores, Last Observation Carried Forward will be used to impute the missing data. For survivorship analysis, the data including implant in situ collected in the next follow-up will be used to calculate survivorship

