#### 2.5. PRIMARY AND SECONDARY ENDPOINTS

Primary endpoint is KSS score at 1 year follow-up.

Secondary endpoints include

- KSS at other follow-up visits
- KOOS, EQ5D, UCLA at 6 month, 1 year, 3 year, 5 year postop
- Radiographic Assessment at Immediate postop, 1 year, 3 year, 5 year postop
- Survivorship up to 10 years

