#### Clinical Assessments

Clinical assessments will include functional scores and radiographic analysis. An operative record will be completed upon the surgery. The operative record will include but are not restricted to date of surgery, surgical approach, and implant components (part number).

Phone Assessment: If a patient will not or is not able to return to the office for a clinical exam, the patient administered outcome forms can be assessed with the patient over the phone. These forms include the KOOS, EQ-5D, UCLA Activity Score, and the Phone Interview (which contains questions on survivorship, KSS Pain, and KSS Function). If the site collects data over the phone, it will be reimbursed at a discounted rate to reflect the uncollected data (KSS Objective and Radiographic Assessment). At the seven and ten year follow-up, it is not required that the patient return for clinical assessment. At minimum, the Phone Interview Form should be collected to document survivorship.

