#### 2.6.2. ASSESSMENT TIMELINES/SCHEDULE

Clinical and Radiographic Exams									
Data Collection item	Pre- operati ve	Intra- operati ve	Immediate Post- operative	6 Months	1 Year	3 years	5 years	7 years	10 years
Demographic and Medical History	Х								
Operative Record		×							
Clinical Evaluation – KSS, KOOS, EQ5D, UCLA	х			х	х	х	х		
Radiographic assessment			х	Х	х	х	х		
Phone Assessment				If Patient will not come to clinic	If Patient will not come to clinic	If Patient will not come to clinic	If Patient will not come to clinic	×	X
Adverse events including revisions		As required							

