#### 2.6.3. ALLOWED WINDOW OF EACH SCHEDULE

Allowed Window of Each Prospective Visit Schedule:

- 6 months (+/- 2 weeks)
- 12 months (+/- 2 months)
- 3 years (+/- 3 months)
- 5 years (+/- 3 months)
- 7 years (+/- 3 months)
- 10 years (+/- 3 months)

Each follow-up visit time point will be determined based on the date of surgery.

Investigators should make their best effort to have patients return in the allotted time window of each milestone. However, in the event that patients return outside of the milestone, the data should still be recorded and reimbursed. Visits will only be reimbursed once per milestone.

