#### 6.5. DATA ANALYSES

The following analyses will be performed:

- 1. Primary Endpoint mean KSS Objective score at 1 year
- 2. Second Endpoints mean KSS Objective score at other postop time points
- 3. Other Clinical Outcomes scores including KOOS, EQ5D and UCLA
- Comparison in clinical outcomes scores between preoperative and various postoperative time points
- 5. Survivorship of Vanguard with endpoint being revisions.

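### Protocol 6.4 fixes last observation carried forward for clinical scores without excluding the pre-operative score, so missing 1-year KSS Objective values can bias the primary mean

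*Protocol*

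**What the plan says.** Protocol 6.4 gives one rule for missing clinical scores: "for clinical outcome scores, Last Observation Carried Forward will be used to impute the missing data". It sets no limit on which observation may be carried and names no other method for these scores.

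Protocol 2.5 says "Primary endpoint is KSS score at 1 year follow-up", and 6.5 specifies it as "Primary Endpoint mean KSS Objective score at 1 year". Section 6.5 also lists "Comparison in clinical outcomes scores between preoperative and various postoperative time points".

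The schedule in 2.6.2 places KSS before surgery and at 6 months, 1 year, 3 years and 5 years. At each of these post-operative visits a phone assessment is allowed: "If Patient will not come to clinic". Section 2.6.1 (Clinical Assessments) says what a phone contact leaves out. The site is paid, but "it will be reimbursed at a discounted rate to reflect the uncollected data (KSS Objective and Radiographic Assessment"). KSS Pain, KSS Function, KOOS, EQ-5D and UCLA can be taken by phone.

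Some provisions limit missing data. Under 2.6.3, "in the event that patients return outside of the milestone, the data should still be recorded and reimbursed". Phone contact is meant for patients who will not or cannot attend, and 6.4 commits to efforts to bring patients back. No expected missing rate is given.

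**The concern.** Only two KSS Objective scores can precede the 1-year visit: the pre-operative one and the 6-month one. The protocol permits the 6-month and 1-year scores both to be missing, for example after two phone contacts. Following 6.4 then has three effects.

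- **Pre-operative score carried.** A measurement taken before the implant is entered as its 1-year result. This pulls the mean down and makes that patient's pre/post change exactly zero in the comparison listed in 6.5.
- **Six-month score carried.** The bias is smaller. It is downward if patients go on improving, and upward if those who stay away have worsened since 6 months. Copied values are also counted as 1-year observations, so the interval is narrower than the observed 1-year data support.
- **Later visits.** At 5 years a 6-month score can stand in 4.5 years after it was taken and hide later change.

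The rule also makes no use of the KSS Pain, KSS Function and KOOS answers from the same phone contact, which could help predict the missing KSS Objective score.

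The study's size rests on the precision of this one mean (6.1), so a bias that is sizeable against the planned half-width undermines the main result. Section 2.4 gives no hypothesis, so what is at stake is the accuracy of the reported mean and interval, not a pass/fail decision.

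**Working it through.** **The plan's own figure.** Section 6.1 gives SD 18 and says "The width of confidence interval is 5 points", so the half-width is 2.5. The confidence level is not stated; taking 95% two-sided:

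n = (1.96 × 18 / 2.5)² = 199.14, which matches the stated 199, rounded to 200. At 90% or 99% confidence the result is 141 or 344, and reading 5 as the half-width gives 50, so 95% with a total width of 5 is the intended reading. At n = 200 the width is 2 × 1.96 × 18 / √200 = 4.99.

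**Inputs for the bias.** From the protocol: SD 18, n = 200, half-width 2.5. Assumed, because the protocol gives no values:

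- G, mean gain from pre-operative to 1 year: 40 points (range 30 to 50)
- g, mean gain from 6 months to 1 year: 5 points (range 3 to 8)
- m, share with no 1-year score
- s, share of those who have a 6-month score

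**Shift per carried score.** Pre-operative: -G/200 = -40/200 = -0.20 points (0.15 to 0.25 in size). Six-month: -g/200 = -5/200 = -0.025 points (0.015 to 0.04). Half of the half-width is 1.25, and 1.25/0.20 = 6.25, so six or seven carried pre-operative scores, about 3% of 200, use it up (five to nine over the range of G).

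**Bias of the mean.** Bias = -m[(1 - s)G + s·g]. For m = 10% and s = 0.9: -0.10 × (0.1 × 40 + 0.9 × 5) = -0.10 × 8.5 = -0.85.

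**Coverage and width.** These come from simulation: 200 cases, 20,000 replicates, SD 18 at every visit, assumed correlations of 0.3 (pre-operative with later scores) and 0.5 (6 months with 1 year), data missing completely at random, t-interval. G = 40 and g = 5 throughout the table.

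| m | s | Bias (formula) | Coverage of 95% CI | CI width, carried forward | CI width, observed only |
|---|---|---|---|---|---|
| 5% | 1 | -0.25 | 94.7% | 5.02 | 5.15 |
| 5% | 0.9 | -0.43 | 93.9% | 5.08 | 5.15 |
| 10% | 1 | -0.50 | 93.2% | 5.03 | 5.29 |
| 10% | 0.9 | -0.85 | 90.0% | 5.15 | 5.29 |
| 10% | 0.75 | -1.38 | 83.4% | 5.31 | 5.29 |
| 10% | 0.5 | -2.25 | 64.7% | 5.57 | 5.29 |
| 20% | 1 | -1.00 | 87.9% | 5.04 | 5.61 |
| 20% | 0.9 | -1.70 | 75.8% | 5.27 | 5.62 |

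Using observed cases only, coverage stayed between 94.7% and 95.2%.

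**Range over G and g.**

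- m = 5%, s = 1: bias from -0.15 (g = 3) to -0.40 (g = 8).
- m = 10%, s = 0.9: bias from -0.57 with coverage about 93% (G = 30, g = 3) to -1.22 with coverage about 85% (G = 50, g = 8).
- m = 10%, s = 0.5: bias from -1.65 to -2.90.

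**Reversal.** If the missing patients had worsened by 3 points since 6 months (g = -3, m = 10%, s = 1), the bias is +0.30 and coverage about 94%.

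**Reading the widths.** When only 6-month scores are carried, the interval is too narrow (5.03 against 5.29 at 10% missing). When many pre-operative scores are carried, it is wider (5.57 against 5.29) because they add spread, and it is centred in the wrong place.

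**The case against.** The strongest reply is that the damage comes mainly from carrying the pre-operative score, and on that 6.4 is merely silent. A statistical analysis plan could restrict carrying to post-operative scores in one line, and 6.4 does not say that no other analysis will be done. Without the pre-operative carry the effect is small: -0.25 points and 94.7% coverage at 5% missing, -0.50 and 93.2% at 10%. The harmful case needs KSS Objective to be missing at both 6 months and 1 year. For 3% of all cases to carry a pre-operative score, 30% of the missing must lack a 6-month score if 10% are missing, or 60% if 5% are missing. The protocol works against this through return efforts, acceptance of late visits and reduced payment for phone data. Every gain, correlation and missing rate above is assumed. The study is single-group with no hypothesis, and a 6-month score reaches 5 years only if 1, 3 and 5 years are all missed, which affects a secondary endpoint.

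Much of this stands. The sizes are conditional, the scenarios with half or a quarter of the missing lacking a 6-month score are pessimistic, and the effect is slight when few are missing and all have 6-month scores. It does not rescue the rule. The protocol itself chooses the method, and applying it as written produces a wrong value in a situation that the protocol's own schedule permits. An analysis plan that followed 6.4 would inherit it. Even with no pre-operative carry, copied scores are treated as 1-year observations.

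**Conclusion.** The concern holds and should be fixed. Section 6.4 fixes a method that can enter a pre-implant score as the 1-year primary outcome and that counts copied scores as observed data.

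In the more plausible range (5% to 10% missing, 90% to 100% of those with a 6-month score, G = 40, g = 5), the bias is -0.25 to -0.85 points, which is 10% to 34% of the 2.5-point half-width, and coverage is about 95% to 90%. The harm grows quickly with the number of pre-operative scores carried: at 10% missing with half of those lacking a 6-month score, the bias of -2.25 is nearly the whole half-width and coverage is about 65%.

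That the rule is stated and reaches the primary endpoint is certain from the text. Its size rests on assumed gains and missing rates. The coverage figures also assume data missing completely at random; phone contact is for patients who will not or cannot attend, so missingness may in fact depend on outcome, and the direction of the bias could then change.

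**What to change.** Replace the clinical-score rule in 6.4 with wording such as:

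> Mean KSS Objective at each visit and its 95% confidence interval will be estimated with a likelihood-based repeated-measures model on all observed scores, or by multiple imputation using earlier KSS Objective scores and the same-visit KSS Pain, KSS Function and KOOS, including those collected by phone. A pre-operative score will never be carried forward as a post-operative outcome.

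The final text should name one of the two methods as primary. Last observation carried forward may stay at most as a sensitivity analysis, from post-operative visits only.

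Both main methods assume data missing at random, so add one simple analysis that relaxes this, for example lowering imputed 1-year scores by 5 and by 10 points (illustrative values that the study team should settle in advance). Report for each visit how many cases have KSS Objective observed, have phone data only, or are missing.

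The cost is one paragraph and slightly more analysis work, with no new data, visits or patients. The interval will reflect the missing data. At 10% missing its width is about 5.3 using observed cases only, against about 5.0 when 6-month scores are copied. A regression estimator using the earlier scores, standing in for the proposed model, gave about 5.2 with no bias and about 95% coverage under data missing completely at random.

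### Does the survivorship missing-data rule in Section 6.4 bias implant survival by back-dating revisions and leaving out patients who never return?

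*Protocol*

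**What the plan says.** Protocol Section 2.5 lists "Survivorship up to 10 years" among the secondary endpoints, and Section 6.5 defines the analysis as "Survivorship of Vanguard with endpoint being revisions". Section 2.7 sets the horizon: "All cases will be followed up to 10 years".

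The missing-data rule is one sentence in Section 6.4: "For survivorship analysis, the data including implant in situ collected in the next follow-up will be used to calculate survivorship".

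Three other places bear on how it works:

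- **Dates.** The schedule in Section 2.6.2 lists revisions under adverse events, to be recorded as required. Section 5 requires a record of every adverse event, "including details of the nature, onset, duration, severity, relationship to the device", and has patients asked about adverse events at each follow-up visit.
- **Late contacts.** Section 2.6.3 says that "in the event that patients return outside of the milestone, the data should still be recorded and reimbursed".
- **Contact at 7 and 10 years.** Under Clinical Assessments in Section 2.6.1 no clinic visit is required then: "At minimum, the Phone Interview Form should be collected to document survivorship".

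The protocol names no survivorship estimator and no censoring rule.

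**The concern.** A rule that takes a missing status from the next visit looks one-sided. If the implant is still in place at the later visit, it was in place at the missed one. If the later visit reveals a revision, copying that status back would count the failure too early, and the gaps between visits from 1 year onward are 2 to 3 years.

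The rule also needs a next visit. A patient who dies, withdraws or is lost has none, and 10 years is the last scheduled contact. If such implants supplied no status while implants already known to be revised still counted as failures, the denominator would shrink selectively and revision would be overstated. Long-term survivorship is the main reason for 10 years of follow-up, so a bias there would matter. With an assumed 5% true revision, 30% loss and 20% missed visits, that reading gives 93.5% survivorship at 10 years against a true 95.0%.

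**Working it through.** The protocol gives no survivorship figure to reproduce. Its one calculated number, 199 cases in Section 6.1, concerns the KSS mean: (1.96 × 18 / 2.5)² = 199.1, with a 95% level assumed. It has no bearing here.

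**Inputs.** From the protocol: visits at 0.5, 1, 3, 5, 7 and 10 years; revision as the event; N = 200. Assumed, because the protocol gives none of them: true 10-year survivorship S(10) = 95% with a constant revision hazard, 20% of visits missed, and loss unrelated to revision. Then S(5) = 0.95^0.5 = 0.9747 and S(7) = 0.95^0.7 = 0.9647.

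**Step 1: what back-dating would do, if it were the rule.** Suppose a missed visit takes the status of the next attended visit, with the 10-year status always obtained.

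- Recorded failure at 7 years = 0.8 × (1 − 0.9647) + 0.2 × (1 − 0.95) = 0.0282 + 0.0100 = 0.0382, so survivorship is 96.2% against a true 96.5%.
- Recorded failure at 5 years = 0.8 × 0.0253 + 0.2 × 0.8 × 0.0353 + 0.2 × 0.2 × 0.05 = 0.0202 + 0.0056 + 0.0020 = 0.0279, so 97.2% against 97.5%.
- In the same way, 3 years gives 98.2% against 98.5%, and 1 year gives 99.2% against 99.5%.

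Over a grid of true 10-year survivorship of 98%, 95% and 90% and missed visits of 10%, 20% and 30%, the largest shift is 0.9 points (90% survivorship, 30% missed). At 10 years the shift is zero, since no later visit exists to copy from. If the recorded onset of the revision is used, it is zero everywhere.

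**Step 2: where 93.5% at 10 years comes from.** Back-dating cannot produce it. With 30% loss and 20% missed visits, unrevised implants with a 10-year status make up 0.95 × 0.70 × 0.80 = 0.532 of the cohort. A result of 93.5% then implies counted revisions of 0.532 × 0.065 / 0.935 = 0.037 of the cohort. So 0.037 / 0.05 = 74% of revised implants are kept, but only 0.532 / 0.95 = 56% of unrevised ones. That unequal retention is the whole of the 1.5-point gap, and no section prescribes it.

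**Step 3: patients missing at 10 years under different treatments.** Let 20% of those at risk after 7 years give no 10-year status.

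- Revised by 7 years: 200 × 0.0353 = 7.05. At risk: 192.9. Missing: 38.6. Observed: 154.4.
- Revisions seen between 7 and 10 years: 154.4 × (1 − 0.95 / 0.9647) = 2.36.

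| Treatment of the 38.6 | Calculation | 10-year survivorship |
|---|---|---|
| Censored at last known status | 0.9647 × (1 − 2.36 / 154.4) | 95.0% |
| Counted as in place | 1 − 9.41 / 200 | 95.3% |
| Dropped | 1 − 9.41 / (200 − 38.6) | 94.2% |
| Counted as revised | 1 − (9.41 + 38.6) / 200 | 76.0% |

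Censoring returns the true value, and nothing in Sections 6.4 or 6.5 excludes it.

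**Step 4: Section 6.4 beside ordinary censoring.** For a patient who misses 3 years and is seen with the implant in place at 5 years, Section 6.4 counts the implant as surviving through 3 years. So does an analysis that censors at the last contact with the implant confirmed in place. For a patient found revised at 5 years, the record holds the onset, and the event goes there. The two agree wherever a later contact exists. Where none exists, Section 6.4 says nothing, which is different from saying that the patient is dropped.

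**The case for a change.** The strongest counter-argument is that Section 6.4 does not leave survivorship to a later plan. It states a rule, and that rule cannot operate after loss, death or withdrawal, or at the final visit. The wording also covers data in general, with the in-place status only as an inclusion, so it is not confined to the case where looking back is valid, and it does not tell the analyst to use the revision date.

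Part of this stands. The sentence is loosely worded, and by itself it cannot supply a status for someone never contacted again. But that makes the rule limited in scope, not wrong. It deals with patients who miss a visit and are reached later; a censoring rule for the rest would supplement it without contradicting it. Permitting a poor reading is also not the same as prescribing one, and the collection of onset dates makes the sound reading the natural one.

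The reach of the gap is also narrower than everyone missing at 10 years: a phone interview suffices at that visit, and data from a late contact are kept. For scale, even complete follow-up of 200 implants at 95% gives a 95% interval of about ±1.96 × √(0.95 × 0.05 / 200) = ±3.0 points. The 1.5-point gap lies inside that and would understate implant survival, not flatter it.

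**Conclusion.** The concern does not hold. Section 6.4 neither assigns later-found revisions to a missed visit nor drops unrevised lost patients. Inference from an implant still in place is exact, and revisions carry an onset. If back-dating were applied all the same, it would move survivorship at 1 to 7 years by about 0.3 points (95% survivorship, 20% missed visits), by at most 0.9 points in the grid examined, and not at all at 10 years. The 10-year figure of 93.5% against 95.0% depends on a dropping rule absent from the protocol and on loss and miss rates the protocol does not give; with censoring the estimate is 95.0%.

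This rests on loss being unrelated to revision and on revision dates being obtained as Section 5 requires. The estimator and the censoring rule for patients with no later contact are not stated. That is detail commonly left to the statistical analysis plan, which is not at hand, so it does not count as an error in the protocol.
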